# **Clinical research protocol**

Project name: The value of critical care ultrasound and noninvasive cardiac output monitoring in guiding fluid resuscitation for septic shock in the emergency department

leading unit:Guangzhou Panyu Central Hospital, Guangzhou, Guangdong, China

project leader:[name]

Department: Emergency Department

Research period: July 2025 to July 2025

Version No.: V 1.0

Version Date: May 22, 2023

|                                      |   |
|--------------------------------------|---|
| object name                          | The value of critical care ultrasound and non-invasive cardiac output monitoring in fluid resuscitation for emergency department patients with septic shock.  |
| goal of study                        | This study explores the value of critical care ultrasound and non-invasive cardiac output monitoring in fluid resuscitation for emergency department patients with septic shock, providing evidence for optimizing hemodynamic management of septic shock, improving patient prognosis, and guiding clinical selection of appropriate monitoring modalities.  |
| research design               | Subjects were recruited from patients with septic shock admitted to the Emergency Department of Guangzhou Panyu District Central Hospital between July 2023 to July 2025. Demographic data of patients, including gender, age, and underlying diseases, were collected, along with mean arterial pressure, baseline lactate levels, and vital signs at enrollment. Records were made of the total fluid volume administered within the first 6 hours after patients were randomized into groups, the achievement of resuscitation targets, blood lactate levels, blood pressure, and the incidence of complications such as pulmonary edema and renal injury. Additionally, the use of vasoactive agents (e.g., dopamine, epinephrine/norepinephrine), mechanical ventilation support, and antibiotics was documented. Patients were followed up to record the duration of emergency department stay, total hospital stay, 28-day mortality, and adverse events occurring during the study period (e.g., severe arrhythmias, anaphylactic shock). |
| Total number of cases studied | 60 cases (30 cases in each group)   |

|                            |   |
|----------------------------|---|
| case selection      | 
Inclusion criteria:
 
(1) diagnosis of septic shock in accordance with the Surviving Sepsis Campaign International; (2) receipt of initial fluid resuscitation in the emergency department with a hospital stay of at least 6 hours; (3) age <math>\geq</math> 18 years; (4) provision of informed consent.
 
excluded criteria:
 
(1) contraindications to rapid fluid administration (e.g., end-stage renal disease, end-stage heart failure, acute pulmonary edema); (2) inability to comply with treatment, such as patients with severe trauma, burns, cancer undergoing chemotherapy, pregnant or lactating women, and those with mental illness; (3) withdrawal from treatment or transfer to another facility within 24 hours of admission.
 |
| Treatment plan      | 
Both groups were managed according to the 2021 Surviving Sepsis Campaign (SSC) International Guidelines for septic shock resuscitation, including: (1) early antimicrobial therapy, (2) vasopressor support (with norepinephrine as first-line), and (3) organ function support. The key difference between groups lay in the fluid resuscitation monitoring approach (critical care ultrasound vs. noninvasive cardiac output monitoring)
   |
| efficacy evaluation | 
The main efficacy indicators: emergency department length of stay, total hospital stay.
 
Secondary efficacy indicators: regarding total fluid volume within the first 6 hours of resuscitation, early resuscitation efficacy (time to achieve mean arterial pressure <math>\geq</math>65 mmHg, lactate reduction <math>\geq</math>20% from baseline, or lactate clearance <math>\geq</math> 10%), complication rates (including pulmonary edema, renal injury, and acute respiratory distress syndrome).
   |

|                           |  |
|---------------------------|--|
|                           | Safety evaluation index: 28-day mortality.   |
| statistical method | 
This study adopted a prospective randomized controlled design, and the sample size was estimated using PASS 15.0 software. Based on the difference in 6-hour fluid resuscitation volume between the two groups in the pilot study (mean difference 1261 mL, standard deviation 3155 mL), <math>\alpha=0.05</math> (bilateral) was set <math>\beta=0.2</math>. Calculated to require 27 cases per group, considering a 20% dropout rate, 60 cases were ultimately included. Use SPSS 26.0 to generate block random sequences (block size 4), and allocate concepts through sealed envelopes. The normality of the measurement data was confirmed by Shapiro Wilk test, and those that conform to the normal distribution were expressed as mean <math>\pm</math> standard deviation. Independent sample t-test was used for inter group comparison; non normally distributed individuals are represented by the median (interquartile range) and Mann Whitney U test is used. The categorical data is presented in terms of the number of cases (%), and the comparison between groups is conducted using the chi square test or Fishers exact test (when the theoretical frequency is less than 5). The main outcome (28 day mortality rate) was plotted using Kaplan Meier survival curve, and inter group differences were analyzed using log rank test, and HR (95% CI) was calculated. Secondary outcomes (such as fluid dosage, MAP, etc.) report mean difference (MD) or relative risk (RR) and their 95% confidence intervals. All tests are bilateral, and <math>P<0.05</math> is considered statistically significant. Perform Bonferroni correction on secondary outcomes (<math>\alpha=0.05/6 \approx 0.008</math>). Multivariate Cox regression was used to adjust for confounding factors such as age and baseline lactate, and sensitivity analysis included protocol set (PP) and intention to treat (ITT) analyses. The statistical software used is R 4.3.1 (R Foundation) and SPSS 26.0 (IBM).
 |

|                        |                        |
|------------------------|------------------------|
| Research period | July 2023 to July 2025 |
|------------------------|------------------------|

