## **(7) standards for efficacy appraisal**

The primary outcome was 28-day mortality

Secondary outcomes included the efficacy of initial resuscitation, duration of hospital stay, incidence of complications, and other relevant parameters.

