## **(10)Statistical processing**

This study adopted a prospective randomized controlled design, and the sample size was estimated using PASS 15.0 software. Based on the difference in 6-hour fluid resuscitation volume between the two groups in the pilot study (mean difference 1261 mL, standard deviation 3155 mL),  $\alpha=0.05$  (bilateral) was set  $\beta=0.2$ , Calculated to require 27 cases per group, considering a 20% dropout rate, 60 cases were ultimately included. Use SPSS 26.0 to generate block random sequences (block size 4), and allocate concepts through sealed envelopes. The normality of the measurement data was confirmed by Shapiro Wilk test, and those that conform to the normal distribution were expressed as mean  $\pm$  standard deviation. Independent sample t-test was used for inter group comparison; non normally distributed individuals are represented by the median (interquartile range) and Mann Whitney U test is used. The categorical data is presented in terms of the number of cases (%), and the comparison between groups is conducted using the chi square test or Fishers exact test (when the theoretical frequency is less than 5). The main outcome (28 day mortality rate) was plotted using Kaplan Meier survival curve, and inter group differences were analyzed using log rank test, and HR (95% CI) was calculated. Secondary outcomes (such as fluid dosage, MAP, etc.) report mean difference (MD) or relative risk (RR) and their 95% confidence intervals. All tests are bilateral, and  $P<0.05$  is considered statistically significant. Perform Bonferroni correction on secondary outcomes ( $\alpha=0.05/6 \approx 0.008$ ). Multivariate Cox regression was used to adjust for confounding factors such as age and baseline lactate, and sensitivity analysis included protocol set (PP) and intention to treat (ITT) analyses. The statistical software used is R 4.3.1 (R Foundation) and SPSS 26.0 (IBM).

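### The protocol names different main outcomes in different places and corrects only the secondary ones; if both stays remain main and either can carry the claim, the false-positive chance is about 7-10%

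*Protocol*

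**What the plan says.** Four places in the protocol bear on which outcome is main.

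- **Synopsis, efficacy evaluation row:** "The main efficacy indicators: emergency department length of stay, total hospital stay". The secondary list in the same row holds 6-hour fluid volume, early resuscitation efficacy and complications, and neither stay. Mortality is placed outside efficacy: "Safety evaluation index: 28-day mortality".
- **Section (7):** "The primary outcome was 28-day mortality". It continues: "Secondary outcomes included the efficacy of initial resuscitation, duration of hospital stay, incidence of complications, and other relevant parameters". ED stay is not named there.
- **Section (10), and the synopsis statistical method row with the same wording:** "The main outcome (28 day mortality rate) was plotted using Kaplan Meier survival curve", with a log-rank comparison.

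The testing rule stands in section (10) and the matching synopsis row. "All tests are bilateral", the threshold is 0.05 per test, and the only correction is "Perform Bonferroni correction on secondary outcomes", with 0.05 divided by 6. The six outcomes behind that divisor are not listed. No section ranks the two stays, splits alpha between them, or says whether one or both must be significant.

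**The concern.** The protocol has a multiplicity rule, so this is not detail left for a later analysis plan. The rule works only if it is clear which outcomes are main and which are secondary. Across the document, three outcomes (ED stay, total hospital stay, 28-day mortality) are called main somewhere, and the correction covers main outcomes nowhere.

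If the disagreement is settled in favour of the synopsis list, two main outcomes remain, each compared with 0.05 and with no rule for combining them. Reporting success on whichever stay crosses the threshold would then be open to the authors, and 0.05 would not limit the chance of a false main claim. Correcting the label alone could leave this gap in place.

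**Working it through.** **Inputs from the protocol.** Two main indicators (synopsis, efficacy evaluation row); two-sided 0.05 per test; Bonferroni for secondary outcomes only (section (10)).

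**Inputs assumed.** The protocol gives no correlation between the two test statistics, so it is varied. ED stay is part of total hospital stay, so a positive value is likely.

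**Step 1: the protocol's own figure.** 0.05 / 6 = 0.0083, which agrees with the stated 0.008. The arithmetic of the secondary correction is right.

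**Step 2: either stay is enough, independent tests.** Under no effect on either stay, P(at least one significant) = 1 − (1 − 0.05)² = 1 − 0.9025 = 0.0975. The sum 0.05 + 0.05 = 0.10 is only an upper bound.

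**Step 3: either stay is enough, correlated tests.** With bivariate normal statistics of correlation ρ, the rate is 1 − P(|Z₁| ≤ c and |Z₂| ≤ c), where c is the two-sided critical value: 1.96 for 0.05 and 2.24 for 0.025.

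| ρ (assumed) | Each at 0.05 | Each at 0.025 |
|---|---|---|
| 0 | 9.75% | 4.94% |
| 0.3 | 9.51% | 4.84% |
| 0.5 | 9.07% | 4.65% |
| 0.7 | 8.35% | 4.30% |
| 0.8 | 7.81% | 4.02% |
| 0.9 | 7.04% | 3.62% |
| 0.99 | 5.66% | 2.86% |

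For ρ from 0 to 0.9 the uncorrected rate runs from about 10% down to 7%. Only with nearly identical tests does it approach 5%. At 0.025 each it stays below 5% throughout.

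**Step 4: both stays must be significant.** P(both significant) cannot exceed P(one given stay significant), so the rate is at most 0.05.

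**Step 5: mortality is the only primary.** One test at 0.05 gives 5%, and no split is needed.

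**Step 6: can the sample size settle the choice?** No. It rests on 6-hour fluid volume ("mean difference 1261 mL, standard deviation 3155 mL"), which the synopsis lists as secondary and no section calls main.

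**The case against.** The strongest reply is that the paragraph setting the 0.05 threshold and the Bonferroni rule itself names a single main outcome, 28-day mortality. Section (7) agrees and makes hospital stay secondary. On that reading there is one main test at 0.05 and a corrected secondary family, which is an ordinary structure. Only the synopsis efficacy row differs. This stands, and it is why the point can only be conditional.

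A reader might go further and infer that the trial's main claim carries an 8-10% error rate in place of a stated 5%. The documents do not support that, for four reasons:

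- It joins the synopsis list to a testing rule written around mortality.
- The rule that either stay suffices is inferred from silence.
- The protocol gives 0.05 as a per-test threshold and promises no family-wise rate, so no stated figure is contradicted.
- The rate falls below 8% once the correlation exceeds roughly 0.75, which is plausible when one stay is part of the other.

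A reader might also count all three outcomes as main and quote 1 − 0.95³ = 14.3%. No section lists the three together as main, and that figure needs independence.

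The reply does not dispose of everything. Section (7) does not name ED stay, except perhaps within its closing catch-all, and the six corrected outcomes are not identified. Even with mortality as primary, nothing expressly places ED stay under the correction while the synopsis still calls it main.

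**Conclusion.** The point holds in conditional form. The firm defect is that the synopsis efficacy row contradicts section (7), section (10) and the synopsis statistical row on the main outcome, while the only multiplicity rule leaves main outcomes uncorrected.

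The 7-10% inflation rests on three assumptions: the synopsis list is the one kept, either stay can carry the claim, and the correlation between the two tests lies between 0 and about 0.9. Drop either of the first two and the rate is at most 5%, provided that what replaces them is a single primary outcome or a requirement that both stays be significant. The protocol as it stands does not tell the reader which case applies.

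**What to change.** Reconcile four places together: the efficacy evaluation and statistical method rows of the synopsis, section (7) and section (10).

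1. Name one primary outcome in the same words in each. If it is mortality, revise its description as a safety index in the synopsis. If it is one of the stays, revise section (7) and the main-outcome wording in section (10).
2. List the outcomes in the Bonferroni-corrected secondary family by name, including ED stay and total hospital stay where not chosen as primary, and make the divisor match the list.
3. If both stays are to remain main, either test each at 0.025 (or by Holm: the smaller p-value against 0.025, then the larger against 0.05), or state that both must be significant at 0.05.

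The cost is a few sentences across these places. Splitting alpha gives each stay a slightly stricter threshold. A stay moved to the secondary family would face about 0.008 if the divisor remains six. Requiring both stays makes a positive main result harder to reach.

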In the critical care ultrasound group, patients underwent immediate bedside assessment using a Philips EPIQ 5 color Doppler ultrasound system equipped with both phased-array (1.5-4.0 MHz) and convex-array (2.0-5.0 MHz) transducers. The initial ultrasound evaluation was completed within 10 minutes of enrollment and included comprehensive hemodynamic monitoring: inferior vena cava diameter (IVC) and collapsibility index (IVC-CI) for volume status assessment, left ventricular ejection fraction (LVEF) and end-diastolic volume (LVEDV) for cardiac function evaluation, ventricular wall motion analysis, along with pulmonary B-line quantification to assess pulmonary edema. This protocol ensured real-time, comprehensive evaluation of both cardiac function and fluid status to guide resuscitation. Ultrasound reassessment was performed every 1-2 hours to dynamically adjust both the volume and rate of fluid administration until predefined resuscitation targets were achieved.

In the noninvasive cardiac output monitoring group, continuous hemodynamic assessment was performed using the NICOM system based on thoracic bioreactance technology. Following the manufacturers standard operating procedures, four electrode pads were placed at bilateral subclavicular areas and the left subcostal region. Monitoring commenced immediately after

enrollment, with baseline parameters recorded after signal stabilization ( $\leq 5$  minutes), including cardiac output (CO), stroke volume (SV), stroke volume variation (SVV), and systemic vascular resistance (SVR). The system automatically updated these parameters every 30 seconds and displayed them in real-time on the monitor screen. Fluid resuscitation was dynamically adjusted according to these continuous measurements until achieving the predefined therapeutic targets.

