### **(6) Observation items and detection time points**

1. Demographic data of patients, including gender, age, and underlying diseases, were collected, along with mean arterial pressure, baseline lactate levels, and vital signs at enrollment.
2. Records were made of the total fluid volume administered within the first 6 hours after patients were randomized into groups, the achievement of resuscitation targets, blood

lactate levels, blood pressure, and the incidence of complications such as pulmonary edema and renal injury.

3. Document the use of vasoactive agents (e.g., dopamine, epinephrine/norepinephrine), mechanical ventilation support, and antibiotics.
4. Record the duration of Emergency Department stay, total hospital stay, 28-day mortality, and adverse events occurring during the study period (e.g., severe arrhythmias, anaphylactic shock).

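### The synopsis defines the MAP outcome as a time to reach 65 mmHg, but the statistics section analyses an undated MAP by mean difference or relative risk, which does not fit that time

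*Protocol*

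**What the plan says.** The efficacy evaluation row of the Protocol synopsis lists, among the secondary indicators, "early resuscitation efficacy (time to achieve mean arterial pressure" of at least 65 mmHg, followed by two lactate criteria joined by an or. The MAP part is a duration.

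Section (10), repeated in the statistical method row of the synopsis, says: "Secondary outcomes (such as fluid dosage, MAP, etc.) report mean difference (MD) or relative risk (RR) and their 95% confidence intervals". MAP has no time point there. Kaplan-Meier, the log-rank test and the HR are tied to 28-day mortality. Secondary outcomes are tested at 0.05/6, about 0.008.

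The other sections do not decide between the two:
- Section (7) says only "Secondary outcomes included the efficacy of initial resuscitation" and names no variable.
- Section (6), like the synopsis design row, section (3) and section (5), lists as recorded "the achievement of resuscitation targets, blood lactate levels, blood pressure". The only resuscitation quantity with a window is the "total fluid volume administered within the first 6 hours after patients were randomized into groups".
- Section (3) adjusts fluids in the ultrasound arm "until predefined resuscitation targets were achieved" but does not list those targets.

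**The concern.** Early resuscitation efficacy is the outcome closest to what the two monitors are meant to change. The protocol states it in one form and describes an analysis for another. That goes beyond detail left to an analysis plan, because any analysis plan would have to depart from one of the two statements.

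Three tests could be defended from the text: a comparison of times, a relative risk for reaching the threshold, and a mean difference in pressure. They answer different questions and differ in their chance of showing a difference. The Bonferroni divisor of 6 counts outcomes; it gives no protection against choosing among forms of a single outcome once the data are known. The data list also does not assure that the time of reaching 65 mmHg is captured.

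**Working it through.** **1. The plan's own figure.** The only stated figure that bears on this outcome is the Bonferroni level: 0.05/6 = 0.0083, given as about 0.008. It reproduces. No effect size or power is stated for MAP.

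**2. Does each stated measure fit the stated endpoint?**
- *Mean difference of times.* A patient who dies first or stays below 65 mmHg has no time, so the mean covers reachers only.
- *Relative risk.* It needs a proportion at a fixed time. That is a different endpoint, and the window is not stated.
- *Mean difference of MAP.* This is a pressure level at an unstated time. Neither the synopsis efficacy row nor section (7) lists it.

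**3. Why dropping non-reachers matters.** Assume exponential times with median m hours, observed for 6 hours.
- Proportion reaching: 1 - 2^(-6/m). For m = 2 this is 87.5%; for m = 4 it is 64.6%.
- Mean over all patients: m/ln 2, giving 2.89 and 5.77 h, a difference of 2.89 h.
- Mean among reachers: m/ln 2 - 6q/(1 - q), with q = 2^(-6/m). For m = 2: 2.885 - 6(0.125)/0.875 = 2.03 h. For m = 4: 5.771 - 6(0.3536)/0.6464 = 2.49 h. The difference is 0.46 h.

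The slower arm loses its longest times, and most of the difference goes with them.

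**4. Power of the forms.** The inputs are 30 per arm (protocol), exponential times and assumed medians. The time form is a Mann-Whitney test with patients not at target by 6 h ranked last. The proportion form is Fisher's exact test if any expected count is below 5, otherwise chi-square. Two-sided 0.05, 6,000 trials per scenario:

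| Assumed medians (h) | Reached by 6 h | Power, time | Power, reached by 6 h |
|---|---|---|---|
| 1 vs 2 | 98% vs 88% | 61% | 11% |
| 1.5 vs 3 | 94% vs 75% | 61% | 43% |
| 1 vs 2.5 | 98% vs 81% | 84% | 40% |
| 1.5 vs 2.5 | 94% vs 81% | 38% | 20% |
| 2 vs 4 | 88% vs 65% | 58% | 56% |

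At 0.05/6 the first row falls to 33% and 2%. Over the five scenarios and repeat runs, the two forms disagree on significance in 24-55% of trials at 0.05 and 14-49% at 0.05/6. A mean difference of times among reachers only has 15-59% power at 0.05, against 37-84% when non-reachers are kept.

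**The case against.** The strongest reply is that the MAP in section (10) is only an example in a list that offers two effect measures. It could be shorthand for time to MAP (a mean difference of times) or for attainment (a relative risk). This stands as far as it goes: a pressure level is the natural reading beside fluid dosage, but not an explicit one. It does not remove the conflict, because under either shorthand the measure still fails to fit a time that some patients never reach.

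Some stronger readings are tempting and are not supported:
- *A third, yes/no definition.* A reader might infer one from "the achievement of resuscitation targets". Those sections list data to record. They define no endpoint, do not name MAP as the target, and are compatible with recording when targets were met.
- *The time cannot be computed.* Blood pressure is listed as recorded, at unstated intervals, so the time may be derivable. It is only not assured.
- *Opposite conclusions.* A constructed data set of 30 per arm can produce them: medians 1.3 vs 2.6 h favour one arm (log-rank p = 0.0056), while mean MAP at 6 h of 67 vs 74 mmHg, SD 8, favours the other (p = 0.0012). That outcome was built in by giving the faster arm the lower pressure. In 10,000 simulated trials, the time and proportion forms were never both significant in opposite directions.
- *A MAP level has only 5% power.* That follows from assuming equal true levels. Treating both arms to a minimum threshold does not make later pressures equal.

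**Conclusion.** The concern holds as a mismatch between the endpoint in the synopsis and the analysis in section (10), together with a data list that does not assure capture of the time. The choice of form can change whether the result is significant: about 24-55% disagreement at 0.05 and 14-49% at 0.05/6 between the time and the proportion by 6 hours. These figures rest on assumed medians, exponential times and a 6-hour window. They show that the choice matters and do not predict this trial's result.

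MAP is one component of one secondary outcome, so the comparison of 28-day mortality is untouched. The passages should be reconciled, at moderate priority.

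**What to change.** State one variable in the synopsis efficacy row, sections (6), (7) and (10), and the synopsis statistical row:
- **Variable:** the synopsis's own measure, time from randomisation to first MAP of at least 65 mmHg.
- **Window:** one stated observation period, for example the 6 hours already used for fluid volume.
- **Analysis:** patients who do not reach the threshold, including those who die, stay in the analysis as not reached. Use a rank or log-rank test with an HR in place of the mean difference or relative risk, at the planned secondary level.
- **Data:** add the time at which the threshold is first reached to section (6).
- **Other forms:** report MAP level and the proportion at target as descriptive only.

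The same edit should say how the MAP time relates to the two lactate criteria joined to it by an or. This concerns outcome measurement only; which resuscitation targets guide treatment is not for this review.

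The cost is wording in these places and one time field. MAP level and the proportion at target lose tested status. No extra patients or procedures are needed.

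### The lactate outcome is defined only through cut-offs although lactate levels are recorded; testing it on its full scale, adjusted for baseline, would recover power in a 60-patient trial

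*Protocol*

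**What the plan says.** The only definition of the lactate outcome is in the synopsis, efficacy evaluation row. It lists "early resuscitation efficacy (time to achieve mean arterial pressure" of at least 65 mmHg, then a "lactate reduction" of at least "20% from baseline, or lactate clearance" of at least 10%. No time point is attached to either lactate cut, and clearance is not defined. Section (7) names the efficacy of initial resuscitation as a secondary outcome without redefining it.

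The measurements are collected. The synopsis (research design) records patient data "along with mean arterial pressure, baseline lactate levels, and vital signs at enrollment", and later "the achievement of resuscitation targets, blood lactate levels, blood pressure". Sections (3), (5) and (6) repeat this. No lactate sampling times are given.

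Section (10) says that for categorical data "the comparison between groups is conducted using the chi square test or Fishers exact test (when the theoretical frequency is less than 5" applies, gives the t-test or Mann-Whitney test for measurement data, and says that secondary outcomes "report mean difference (MD) or relative risk (RR) and their 95% confidence intervals". It does not say which of these applies to lactate. Secondary outcomes are tested at 0.05/6, about 0.008.

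**The concern.** A threshold treats unlike patients alike. With the 20% cut, a fall of 21% and a fall of 70% at the same blood draw score the same, while falls of 19% and 21% score as opposites. This holds if the outcome is target attainment, and also if the opening time-to-target wording is meant to cover lactate, because the event is still the crossing of a cut.

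Lactate is the perfusion measure among the listed outcomes, and section (1) of the Protocol makes tissue hypoperfusion and the first 6 hours central. With 30 patients per arm and a secondary threshold near 0.008, there is little information to give away. The Protocol gives no reason for testing on either cut.

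**Working it through.** **What the plan supplies.** It states no lactate effect, SD, response rate or power, so there is no lactate figure to reproduce. Inputs taken from it:
- 30 per group (synopsis). Section (3) speaks of 73 randomised participants; 30 per arm is used here.
- Two-sided alpha 0.05, and 0.05/6 for secondary outcomes (section (10)).
- Its only effect size, for 6-hour fluid volume: 1261/3155 = 0.40. Using it for lactate is an assumption.

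Other assumptions: log-lactate change is normal with equal variance in the arms; 50, 60, 70 or 80% of the poorer arm reaches the cut. The value 0.74 is the standardised difference that gives 80% power on the full scale at 30 per arm. It is a reference point, not a forecast.

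**Method.** For a shift d and poorer-arm response p1, the better arm responds with p2 = Φ(Φ⁻¹(p1) + d). Example: d = 0.40 and p1 = 0.70 give Φ(0.524 + 0.40) = Φ(0.924) = 0.82. Power on the cut comes from enumerating all outcomes of two binomials of size 30, with chi-square, or Fisher when an expected count is below 5. Full-scale power is the exact two-sample t-test. As a check, the normal approximation at d = 0.40 is Φ(0.40 × √15 − 1.96) = Φ(−0.41) = 34%, against 33% exact.

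**Power of the full scale and of the cut**

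| alpha | d | full scale | cut, at 50 / 60 / 70 / 80% response | loss (points) |
|---|---|---|---|---|
| 0.05 | 0.20 | 12% | 10 / 9 / 9 / 6% | 2-6 |
| 0.05 | 0.30 | 21% | 15 / 14 / 13 / 9% | 6-12 |
| 0.05 | 0.40 | 33% | 23 / 21 / 19 / 12% | 10-21 |
| 0.05 | 0.74 | 80% | 59 / 55 / 45 / 25% | 22-55 |
| 0.05/6 | 0.20 | 3% | 2 / 2 / 2 / 1% | 1-2 |
| 0.05/6 | 0.30 | 7% | 4 / 4 / 3 / 2% | 3-5 |
| 0.05/6 | 0.40 | 13% | 7 / 7 / 6 / 3% | 6-10 |
| 0.05/6 | 0.74 | 56% | 32 / 28 / 21 / 9% | 24-47 |

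**Which full-scale analysis.** The table tests change in log lactate. Let r be the correlation between baseline and 6-hour log lactate, with equal variances (assumed; the Protocol gives none). The same effect then becomes:
- unadjusted 6-hour level: d × √(2(1 − r));
- 6-hour level adjusted for baseline: d × √(2(1 − r)/(1 − r²)) = d × √(2/(1 + r)).

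Power at 30 per arm, alpha 0.05:

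| d | r | unadjusted level | adjusted for baseline |
|---|---|---|---|
| 0.40 | 0.3 | 44% | 47% |
| 0.40 | 0.7 | 22% | 38% |
| 0.40 | 0.8 | 16% | 36% |
| 0.74 | 0.3 | 92% | 94% |
| 0.74 | 0.7 | 59% | 86% |
| 0.74 | 0.8 | 43% | 84% |

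At r = 0.7 the unadjusted level does no better than the cut when 50% respond (22% against 23%; 59% against 59%). At r = 0.8 it does worse than the cut at 50-70% response (16% against 19-23%; 43% against 45-59%). The adjusted analysis exceeds the cut in every row.

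**The case against.** The strongest reply is that no sentence says lactate will be analysed only as yes/no. The synopsis definition opens with a time to reach a target, which may cover all three criteria, and a time is not a chi-square outcome. Section (10) names MAP beside fluid dosage as a secondary outcome, although the synopsis defines MAP, too, only through a cut; a cut in the synopsis therefore does not prove that the measurement is discarded. Lactate levels are listed apart from target attainment, mean differences are allowed, and the scale may be settled in an analysis plan that is not shown.

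Most of this stands. A reader might infer that lactate is analysed solely as a binary outcome, and the documents do not support that. What remains is that the synopsis fixes the outcome, and fixes it through cuts under each reading. Being recorded does not make lactate level a listed outcome, and the open-ended wording of section (7) adds nothing specific. If the time reading is intended, the power figures do not apply directly, but the result still depends on the cut.

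Two further replies are sound. Lactate is one component of one secondary outcome and the trial was not sized on it, so no stated power is lost. And an unadjusted 6-hour level could lose power relative to the cut, which is why the fix includes baseline lactate.

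**Conclusion.** The lactate outcome is badly fixed: its only definition rests on thresholds while the underlying measurement is recorded. Should attainment be tested as categorical data, the loss at alpha 0.05 is about 10-21 points at a standardised difference of 0.40 and 22-55 points at 0.74; at 0.05/6 it is 6-10 and 24-47 points. These figures assume 30 per arm, normal log-lactate change and 50-80% response in the poorer arm.

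A reader might take from this that a cut always costs at least 5 points of power here. That does not follow. The Protocol gives no lactate effect, and at 0.05/6 the loss is only 1-5 points for differences of 0.2-0.3, where full-scale power is 3-7%. Even at 0.40 and 0.05/6, full-scale power is only 13%. The gain matters chiefly if the true lactate difference is moderate to large. The point is a cheap improvement to a secondary outcome, and does not threaten the trial's main comparison.

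**What to change.** In the synopsis (efficacy evaluation) and section (10), make the tested lactate outcome log lactate at the end of the 6-hour resuscitation period, compared between arms by a linear model adjusted for log baseline lactate, and reported as a ratio of geometric means with its 95% CI. State the 6-hour lactate sampling time in section (6), which now gives none. Report attainment of the lactate target as n (%) without its own significance test. Keep the baseline adjustment as part of the change, because the unadjusted 6-hour level may do no better than the cut.

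The cost is a wording change in these places and a fixed sampling time. Baseline and later lactate are already recorded, but the Protocol does not say that a sample is drawn at 6 hours, so one may have to be scheduled. The small downside is that the easily read responder percentage becomes descriptive.
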